7.6.4.8. Nodule Consistency – Responder Analyses

7.6.4.8.1. Participant Level Analyses: Change in consistency from Baseline to Day 15, 29, 43 and 57 in the Nodule Consistency

The difference in proportion of responders between EN3835 and placebo will be analyzed using CMH test stratified by baseline nodule consistency separately for each visit.

The stratum adjusted risk difference, associated 95% CI and p-value will be presented separately for each visit. The frequency and percentage of responders (Section 4.6.1) and 95% CI will be provided based on the Wilson (Score) by treatment group and visit (ie, Days 15, 29, 43, and 57).

The degree of improvement in nodular consistency will be summarized using frequency and percentages with mean and SD by each treatment group and visit (ie, Days 15, 29, 43, and 57).

A listing of nodule consistency will be provided by participant.

7.6.4.8.2. Nodule Level Analyses: Change in consistency from Baseline to Day 15, 29, 43 and 57 in the Nodule Consistency

The difference in proportion of responders between EN3835 and placebo will be analyzed using CMH test stratified by baseline nodule consistency separately for each visit and each nodule.

The stratum adjusted risk difference, associated 95% CI and p-value will be presented separately for each visit. The frequency and percentage of responders (Section 4.6.1) and 95% CI will be provided based on the Wilson (Score) by treatment group and visit (ie, Days 15, 29, 43, and 57).

The degree of improvement in nodular consistency will be summarized using frequency and percentages with mean and SD by each treatment group and visit (ie, Days 15, 29, 43, and 57) for each treated nodule.

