7.5. Measures to Minimize Bias

This is a double-blind, placebo-controlled study. Participants will be randomized according to a validated, computer generated allocation scheme to receive the study interventions described in a 1:1 ratio. Participants will complete their assessment scales before the investigator scales will be completed to avoid bias. Precautions will be in place to ensure that investigators are blinded to participant assessments on the COA scales.

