10. STATISTICAL CONSIDERATIONS AND METHODS

10.1. Sample Size Determination

The primary endpoint is the difference between EN3835 and placebo in the mean change from Baseline (Day 1) to Day 57 on the foot pain subscale (total score on 9 items) of the FFI ranging from 0 ("None") to 4 ("Extreme").

The sample size was estimated based on an interim analysis of the Day 57 data from Study EN3835-105, a dose-finding Phase 1 study. Assuming a difference in the mean change from Baseline to Day 57 in the pain subscale of FFI between EN3835 and placebo of 5.0 with a 10 standard deviation and 85% statistical power using a 2-sided test ($\alpha = 0.05$), 73 participants per treatment group (146 in total) will be needed to detect this difference between the 2 treatment groups. Assuming a dropout rate of 15%, the total sample size will be 172, eighty-six per treatment group for the study.

Participants will be screened to ensure that approximately 172 participants are randomized into 2 treatment groups, an EN3835 group and a placebo group in a 1:1 ratio.

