4.6. Nodule Assessments

4.6.1. Nodular Consistency of the Selected Nodule

The investigator will classify the nodule as “hard”, “firm throughout”, “moderately firm”, “soft” or “non-palpable” at scheduled visits as per the SoA ([Table 2](#)). All nodule level assessment will be captured in the eCRF.

A participant-level responder is defined as a participant with at least 1-level reduction in nodular consistency from baseline for any treated nodule at follow-up visits. The corresponding baseline value will be used as a controlling factor for the responder analyses.

A foot-level responder is defined as a participant with at least 1-level reduction in nodular consistency from baseline for any treated nodule in that foot at a follow-up visit. The corresponding baseline value will be used as a controlling factor for the responder analyses.

A nodule-level responder is defined as a treated nodule with at least 1-level reduction in nodular consistency from baseline at a follow-up visit. The corresponding baseline value will be used as a controlling factor for the responder analyses.

For participant level classification of nodule in demographic/baseline characteristics table and listing, worst case approach will be used.

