Exploratory	The difference in the proportion of participants treated with EN3835 or placebo reporting Minimal Improvement (+1), Much Improvement (+2), and Very Much Improvement (+3) on the activity limitation subscale of the PGIC scale, a 7 point scale ranging from -3 (“Very Much Worse”) to +3 (“Very Much Improvement”) on Days 15, 29, 43, and 57.	Cochran-Mantel-Haenszel method (mITT)			
Exploratory	The difference between EN3835 and placebo in the mean change from Baseline (Day 1) to Day Days 15, 29, 43, and 57 on the Pain Intensity NRS, ranging from 0 (“None”) to 10 (“Worst Pain Imaginable”) with EN3835 vs placebo.	MMRM based on (Observed Data) (mITT)			
Exploratory	The difference in the proportion of participants treated with EN3835 or placebo reporting to be “Satisfied” (+1) and “Very Satisfied” (+2) on the Subject Satisfaction With Treatment Scale, a 5-point scale ranging from -2 (“Very Dissatisfied”) to +2 (“Very Satisfied”) on Days 15, 29, 43, and 57.	Cochran-Mantel-Haenszel method (mITT)			
Exploratory	The difference between EN3835 and placebo in the mean change from Baseline (Day 1) to Day Days 15, 29, 43, and 57 on the activity limitation subscale (total score on 3 items) of the FFI, ranging from 0 (“Never”) to 4 (“Always”).	MMRM based on (Observed Data) (mITT)			
Exploratory	The difference between EN3835 and placebo in the mean change from Baseline (Day 1) to Days 15, 29, 43, and 57 on the difficulty subscale (total score on 9 items) of the FFI, ranging from 0 (“No Difficulty”) to 4 (“A Lot of Difficulty”).	MMRM based on (Observed Data) (mITT)			

Table 27: List of Analyses Performed on All Efficacy Endpoints (Continued)

Endpoint (Primary/ Secondary /Exploratory)	Endpoint	Primary analyses	Subgroup Analyses	Sensitivity Analyses	Supportive Analyses
Exploratory	The difference between EN3835 and placebo in the mean change from Baseline (Day 1) to Days 15, 29, 43, and 57 in the nodule size of the treated nodules by caliper measurements.	MMRM based on (Observed Data) (mITT)			Nodule level analyses - MMRM (Observed Data) (mITT)
Exploratory	The difference between EN3835 and placebo in the change in nodule consistency from Baseline (Day 1) to Days 15, 29, 43, and 57 as determined by the number of participants with a soft or non-palpable consistency at Day 57.	Cochran-Mantel-Haenszel method (mITT)			Nodule level analyses: Cochran-Mantel-Haenszel method (mITT)

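### SAP 7.6.4.8.2 leaves open whether nodules are pooled or tested by number; if pooled, its CMH test and Wilson intervals ignore that nodules share a participant

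*SAP*

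**What the plan says.** SAP 4.6.1 sets the unit of response: "A nodule-level responder is defined as a treated nodule with at least 1-level reduction in nodular consistency from baseline at a follow-up visit". SAP 7.6.4.8.2 then compares the arms with a "CMH test stratified by baseline nodule consistency separately for each visit and each nodule". Its next sentences present the stratum-adjusted risk difference, CI and p-value by visit, and the Wilson intervals by treatment group and visit. Neither mentions the nodule. The closing descriptive summary is again given nodule by nodule. The section names no GEE, random effect, cluster-robust variance or clustered form of CMH.

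Table 27 in SAP 7.6 lists the analysis in its supportive column, for an exploratory endpoint: "Nodule level analyses: Cochran-Mantel-Haenszel method (mITT" population).

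On the structure of the data, Protocol 7.5 states: "Participants will be randomized according to a validated, computer generated allocation scheme to receive the study interventions described in a 1:1 ratio". Protocol 5.2 allows several nodules to be treated on one foot. The exclusion criteria in Protocol 6.2 limit a participant to four nodules in total (three in unilateral disease, two per foot in bilateral disease).

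**The concern.** All nodules of a participant receive the same randomized treatment. They share the same disease and, where the site can manage it, the same assessor (Protocol 9.1.1.2 asks for this effort but does not guarantee it). Their responses are therefore likely to be positively correlated. A CMH test on pooled nodules counts each nodule as independent information and so understates the error. A Wilson interval on the pooled proportion in each arm has the same fault.

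The SAP handles this elsewhere. The nodule-level models for hardness (7.6.3.3.2) and size (7.6.4.7.2) name nodules as well as visits as repeated measures. Consistency, the binary outcome, has no equivalent provision.

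At stake is a nodule-level result that could look significant, or more precise than it is, beside a participant-level result that does not.

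**Working it through.** **Step 1. The plan's own figure.** The documents give no figure for this analysis. The trial size is checked because it supplies the number of participants used below. Protocol 10.1 assumes this effect: "difference in the mean change from Baseline to Day 57 in the pain subscale of FFI between EN3835 and placebo of 5.0". Its other inputs are an SD of 10, power of 85% and a two-sided alpha of 0.05.

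- Normal approximation: n = 2 × (1.960 + 1.036)² × 10² / 5² = 71.8, so 72 per arm.
- Two-sample t-test: 72.8, so 73 per arm. This matches "73 participants per treatment group (146 in total) will be needed to detect this difference between the 2 treatment groups".
- Dropout: 73 / 0.85 = 85.9, so 86 per arm and 172 in total. This matches "Assuming a dropout rate of 15%, the total sample size will be 172, eighty-six per treatment group for the study".

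The stated sample size reproduces. The checks below use 73 participants per arm.

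**Step 2. Nodules pooled within a visit.** With treatment assigned by participant and m nodules per participant:

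- DEFF = 1 + (E[m²]/E[m] − 1) × ICC
- actual two-sided error = 2 × (1 − Φ(1.96/√DEFF))
- CI coverage = 1 − actual error

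The shares of participants with 1/2/3/4 nodules and the ICC are assumptions:

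- 75/20/4/1%: E[m] = 1.31, E[m²] = 2.07, ratio 1.580
- 58/27/12/3%: E[m] = 1.60, E[m²] = 3.22, ratio 2.013
- 35/30/25/10%: E[m] = 2.10, E[m²] = 5.40, ratio 2.571

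Example for the first row at ICC 0.2: DEFF = 1 + 0.580 × 0.2 = 1.116, √DEFF = 1.056, error = 2 × (1 − Φ(1.856)) = 6.4%.

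| Mean nodules | DEFF, ICC 0.2 to 0.8 | True SE larger by | Actual error | 95% CI coverage |
|---|---|---|---|---|
| 1.3 | 1.12 to 1.46 | 6% to 21% | 6.4% to 10.5% | 93.6% to 89.5% |
| 1.6 | 1.20 to 1.81 | 10% to 35% | 7.4% to 14.5% | 92.6% to 85.5% |
| 2.1 | 1.31 to 2.26 | 15% to 50% | 8.7% to 19.2% | 91.3% to 80.8% |

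A simulation of the pooled CMH agrees. It used 73 participants per arm, three baseline-consistency strata, 40% response in both arms and 5,000 runs per scenario. The type I error at binary ICC 0.33 / 0.59 / 0.80 was:

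- mean 1.3: 6.8% / 8.8% / 11.0%
- mean 1.6: 9.5% / 12.2% / 14.5%
- mean 2.1: 11.9% / 16.2% / 20.2%

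With ICC 0 it was 5.1% to 5.2%, so the excess comes from clustering.

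**Step 3. One test per nodule number.** Each test then holds at most one nodule per participant, so DEFF = 1. Simulating one nodule per participant with 73 per arm gave an error of 5.0% in 60,000 runs. The difficulty is different: tables become sparse. Under the same assumed distributions, the expected number per arm with a third nodule is 73 × 0.05 = 3.7, 73 × 0.15 = 11.0 or 73 × 0.35 = 25.6. With a fourth it is 0.7, 2.2 or 7.3. Each is then split over three baseline strata (hard, firm throughout, moderately firm). Up to 4 nodule numbers at 4 visits gives up to 16 tests.

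**Step 4. Which nodule count is plausible.** Protocol 3.2.1 gives only percentages from the earlier study. In a group of 8 participants, 72.7% of nodules fits 8/11, or 11/8 = 1.4 nodules per participant. This is an inference, but it points to the lower rows of the range.

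**The case against.** A reader might infer that the nodule-level CI and p-value are definitely wrong. The documents do not support that. Read literally, the analysis sentence gives each nodule its own test, and Step 3 shows such a test has no clustering problem. The closing summary fits that reading. The by-visit presentation sentence also appears in the participant-level section (7.6.4.8.1) and may simply have been carried over. The table layouts and code are in SAP Module 2 (SAP 10 and 11), which is not among these documents and might settle the matter.

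A reader might also infer that the trial's conclusions are at risk. They are not. Protocol 10.3.1 bases interpretation on participant-level results and calls nodule-level results supportive. The endpoint is exploratory and lies outside the testing hierarchy, with nominal p-values only.

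The higher error rates also need generous inputs. Four nodules require two on each foot, and the injection limits then require each to be no larger than 2 cm. Protocol 3.1 cites bilateral disease in 25% of patients.

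All of this stands and limits the point. It does not make the section well specified. The literal reading leaves nodule 1 with no stated meaning across participants, and it conflicts with results presented only by visit. A supportive role does not make a stated 95% CI correct if nodules are pooled.

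**Conclusion.** The point holds as a conditional one, of minor severity. SAP 7.6.4.8.2 is internally inconsistent, and neither reading gives a sound, fully specified analysis:

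- **Pooled:** the CIs, including the Wilson intervals, are too narrow and the p-values too small. The error is about 6% to 11% at a mean of 1.3 nodules per participant and up to about 20% at 2.1.
- **By number:** each test is valid as regards clustering but rests on an arbitrary label and, for later nodules, on sparse tables.

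The sizes depend on assumed nodule distributions, an assumed ICC of 0.2 to 0.8 and positive within-participant correlation. If most participants have one nodule, the inflation is modest.

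**What to change.** Replace the analysis and presentation sentences of SAP 7.6.4.8.2, and the matching entry in Table 27, with one nodule-level analysis per visit that clusters on participant. Either of these will do:

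- a cluster-adjusted Mantel-Haenszel risk difference stratified by baseline consistency; or
- a GEE with participant as cluster and robust SE, including treatment and baseline consistency. Use an identity link, or a logit link with a marginal standardized risk difference if the identity link does not converge. The fallback should be written in now, because Protocol 3.2.1 reports 72.7% to 90% of nodules improving after initial treatment, and identity-link models can fail at high response rates.

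Replace the nodule-level Wilson intervals with cluster-robust ones. Alternatively, report nodule-level consistency descriptively, with no CIs or p-values.

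The cost is revised SAP text, some programming and a somewhat wider CI. No data collection and no other analysis changes.

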7.6.5. Subgroup Analysis

The primary, key secondary, and frequency of TEAEs will be performed for the following subgroups:

1. Number of injections (1 vs 2 vs 3 vs 4) at Day 1

2. Baseline FFI Total Pain Subscale Score: Group 1 vs Group 2

- a. Group 1: FFI total pain subscale score ≤ 20 for participants without orthotics or FFI total pain subscale score ≤ 26 for participants with orthotics
- b. Group 2: FFI total pain subscale score ≥ 21 for participants without orthotics or FFI total pain subscale score ≥ 27 for participants with orthotics

Subgroups may be combined with adjacent groups (which have less number of participants until count of participant exceeds 10). if the number of participants in that group is less than 10.

The subgroup analyses will be tabulated similar to primary analyses for primary endpoint and key secondary endpoints (Section 7.6.1.2 for 1st and 3rd Key secondary endpoints and Section 7.6.3.2.1 for 2nd key secondary endpoint).

Incidence of TEAEs will be tabulated with risk difference and confidence interval using subgroups (Section 7.7.2).

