10.7. Subgroup Analysis

Analysis for primary endpoint, key secondary endpoints, and frequency of TEAEs will be performed in the following subgroups.

1. Number of injections (1 vs 2 vs 3 vs 4)
2. Baseline FFI pain subscale score: Group 1 vs Group 2
 - a. Group 1: subscale score ≤ 20 for participants without orthotics or subscale score ≤ 26 for participants with orthotics
 - b. Group 2: subscale score ≥ 21 for participants without orthotics or subscale score ≥ 27 for participants with orthotics

Subgroups maybe be combined with adjacent groups if the number of participants in that group is less than 10.

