6.4. Subgroup Analyses

Exploratory subgroup analyses will be performed on the primary endpoint, key secondary endpoints, and frequency of TEAE. The subgroups are:

1. Number of injections (1 vs 2 vs 3 vs 4) at Day 1
2. Baseline FFI Total Pain Subscale Score: Group 1 vs Group 2
 - a. Group 1: FFI total pain subscale score ≤ 20 for participants without orthotics or FFI total pain subscale score ≤ 26 for participants with orthotics
 - b. Group 2: FFI total pain subscale score ≥ 21 for participants without orthotics or FFI total pain subscale score ≥ 27 for participants with orthotics

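### SAP 7.6.5 gives each subgroup its own p-value, and nothing in the visible text compares the treatment effect between subgroups

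*SAP*

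**What the plan says.** Protocol 10.7 introduces the subgroups: "Analysis for primary endpoint, key secondary endpoints, and frequency of TEAEs will be performed in the following subgroups". SAP 6.4 gives their status: "Exploratory subgroup analyses will be performed on the primary endpoint, key secondary endpoints, and frequency of TEAE". There are two factors. One is "Number of injections (1 vs 2 vs 3 vs 4) at Day 1"; the other splits participants into two groups by baseline FFI pain score, with cut-offs that depend on orthotics use. Levels with fewer than 10 participants may be merged with a neighbouring level.

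The method in SAP 7.6.5 is one sentence: "The subgroup analyses will be tabulated similar to primary analyses for primary endpoint and key secondary endpoints". Table 27 agrees, listing ANCOVA (ITT) as the subgroup method for the primary endpoint and key secondary endpoints 1 and 3, and CMH (ITT) for CGIC. The ANCOVA in SAP 7.6.1.1 contains treatment, baseline score, maximum nodule dimension and number of nodules. It yields an LS mean difference, 95% CI and p-value. The CMH analysis in SAP 7.6.3.2.1 yields a stratum-adjusted risk difference, CI and p-value. TEAEs by subgroup get a risk difference and CI.

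None of these sections contains a treatment-by-subgroup term, a homogeneity test or a rule for reading the subgroups, and SAP 7.6.5 is not redacted. Where the SAP wants an interaction it names one: the nodule-level MMRMs in 7.6.3.3.2 and 7.6.4.7.2 list treatment by visit.

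**The concern.** A subgroup table is usually read to see whether the effect is consistent across levels. A p-value inside each level does not measure that. It depends heavily on how many participants fall in the level, so equal true effects can give unequal p-values, and chance alone can produce an isolated significant level in a trial with no effect. The Protocol's summary of changes says the subgroup analyses were added at the FDA's request, so they will have readers outside the sponsor. At stake is the reading of consistency by nodule burden and baseline pain. The primary and key secondary inferences are not affected.

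**Working it through.** **Inputs from Protocol 10.1.** Effect and SD: "between EN3835 and placebo of 5.0 with a 10 standard deviation and 85% statistical power". Test and evaluable size: "using a 2-sided test ($\alpha = 0.05$), 73 participants per treatment group (146 in total) will be needed". Randomized size: "Assuming a dropout rate of 15%, the total sample size will be 172, eighty-six per treatment group for the study". The subgroup factors have 4 and 2 levels (SAP 7.6.5).

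**Assumptions.** The documents give no level sizes. I use equal splits and, for injections, a 45/30/15/10% split, with 73 or 86 analysed per arm. Tests are unadjusted two-sample t-tests with SD 10.

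**1. The plan's own figure.** Noncentral-t power is 84.6% at 72 per arm and 85.1% at 73, so 73 is reproduced. 73/0.85 = 85.9, rounded up to 86 per arm and 172 in total. This agrees with the plan.

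**2. Uniform effect of 5.0.** Let p_k be the t-test power in level k, with n_k participants per arm. The levels of one factor are disjoint, so P(all significant) = Πp_k, P(none) = Π(1 − p_k), and P(mixed) = 1 − Πp_k − Π(1 − p_k).

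| Levels (assumed split) | Analysed per arm | Power per level | All | None | Mixed |
|---|---|---|---|---|---|
| 2 equal | 73 | 56% each | 31% | 19% | 49% |
| 2 equal | 86 | 63% each | 40% | 14% | 47% |
| 4 equal | 73 | 31% each | 1.0% | 22% | 77% |
| 4 equal | 86 | 36% each | 1.7% | 17% | 82% |
| 45/30/15/10 | 73 | 51, 37, 20, 14% | 0.5% | 21% | 78% |
| 45/30/15/10 | 86 | 58, 42, 23, 16% | 0.9% | 16% | 84% |

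Example, two equal groups at 86 per arm: 2 × 0.63 × 0.37 = 0.466. With an 80/20 pain split the mixed probability is about 63%. Under the 45/30/15/10 split the smallest level holds 0.10 × 146 = 14.6 to 0.10 × 172 = 17.2 participants, so the merging rule would not apply.

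**3. No effect, primary endpoint, six tests.** If the tests were independent, P(any p < 0.05) = 1 − 0.95^6 = 26.5%, and P(any favouring EN3835) = 1 − 0.975^6 = 14.1%. The two factors divide the same participants, so the tests are correlated. Simulation at 86 per arm gives 24-25% for either direction and 12-13% favouring EN3835. Among null trials whose primary result is non-significant, the figures are 21.5% and 11%.

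**4. What an interaction test can deliver.** Under a uniform effect it signals heterogeneity at its nominal 5% per factor. For two equal pain groups its SE is 10 × √(2/n + 2/n), with n per arm per group:

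- n = 36.5: SE 3.31. Power for a true 5-point difference in effect is Φ(5/3.31 − 1.96) = 33%.
- n = 43: SE 3.05. Power is Φ(5/3.05 − 1.96) = 37%.

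For 80% power the effects would have to differ by (1.96 + 0.84) × SE, which is 8.5 to 9.3 points.

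**The case against.** The best defence is that the SAP treats these tables as exploratory, keeps them outside the hierarchy of SAP 6.5 and says only that they will be tabulated. The planned output includes estimates and CIs, which allow a sensible descriptive reading, and describing the effect at each level is a legitimate purpose in itself. The mixed pattern arises only for a reader who sorts levels by p < 0.05. All of this stands, and it limits the point to an omission in exploratory reporting. It does not explain why p-values should be printed within levels while the between-level comparison is left out.

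A reader might go further in four ways that the documents do not support:

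- *That the plan judges subgroup effects by significance.* No section states such a rule.
- *That the tables will decide which nodule burden or pain level goes forward.* Neither document says so; the only stated origin is the FDA request.
- *That a null trial will often show a positive subgroup.* The 24% counts both directions; about 12% favour EN3835. Counting all four endpoints (24 tests) gives 34-35% favourable, but only under an assumed between-endpoint correlation of 0.5.
- *That the one-injection level breaks the model.* Every nodule must be treated and takes at least one injection, so nodule count is constant there. The covariate simply drops out and the CMH becomes unstratified; neither biases the estimate.

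The interaction test is also weak, and its p-value without a caution would invite the opposite error. That objection is right, and the fix allows for it.

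**Conclusion.** The point holds as an omission: the visible plan produces a p-value inside each subgroup level and no comparison between levels. If those p-values are compared under the design effect, a mixed pattern appears in about 77-84% of trials across four injection levels and about 47-49% across two equal pain groups. In a null trial at least one of the six primary-endpoint tests has p < 0.05 in about 24% of trials, and about 12% show one favouring EN3835.

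These figures rest on assumed level sizes and on unadjusted tests with SD 10. Covariate adjustment would raise power to the extent that it explains variance. Merging small levels would reduce the number of tests. The imputation steps in SAP 7.6.1.2 are redacted and the Module 2 shells are not available, so an interaction row there cannot be excluded; the SAP text does not call for one.

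**What to change.** Amend SAP 6.4, 7.6.5 and Table 27 before database lock:

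- **Primary endpoint and key secondary endpoints 1 and 3:** for each subgroup factor, fit one ANCOVA to the full ITT imputed data, adding subgroup and treatment-by-subgroup terms to the planned model. Report the LS mean difference and 95% CI for each level, and the interaction estimate with its CI and p-value, combined by Rubin's rules. The four-level factor has three interaction contrasts and needs a joint test.
- **CGIC:** report the risk difference and CI for each level, with a test of homogeneity across levels.
- **Both:** omit the within-subgroup p-values and label the results descriptive. State that interaction power is low, about 33-37% for a 5-point difference between equal pain groups, so a non-significant interaction does not show homogeneity.

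The cost is SAP wording and a changed table shell. No further data are needed.
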